### 4.2.2. Additional Exclusion Criteria for Dose Finding Part

15. Has multiple primary malignancies within 3 years, except adequately resected non-melanoma skin cancer, curatively treated in-situ disease, or other solid tumors curatively treated.

### 4.2.3. Exclusion Criteria for Dose Expansion Part

Subjects who meet any of the following criteria will be disqualified from entering the study in the Dose Expansion Part:

- 1. Prior treatment with an anti-HER3 antibody.
- 2. Prior treatment with an antibody-drug conjugate (ADC) which consists of a topoisomerase I inhibitor, exatecan derivative (eg, DS-8201a) or govitecan derivative (eg, IMMU-132).
- 3. Has a medical history of symptomatic CHF (New York Heart Association [NYHA] classes II-IV) or serious cardiac arrhythmia requiring treatment.
- 4. Has a medical history of myocardial infarction or unstable angina within past 6 months prior to enrollment.
- 5. Has any clinically important abnormalities in rhythm, conduction or morphology of resting ECG, eg, complete left bundle branch block, third-degree heart block, second-degree heart block, or PR interval >250 ms.
- 6. Has a mean QTcF prolongation to >450 ms in males and >470 ms in females in 3 successive screening measurements as assessed by central laboratory.
- 7. Has any factors that increase the risk of QTc prolongation or risk of arrhythmic events, such as congenital long QT syndrome, family history of long QT syndrome or unexplained sudden death under 40 years of age in first-degree relatives.
- 8. Has any history of interstitial lung disease (including pulmonary fibrosis or radiation pneumonitis), has current ILD/pneumonitis, or is suspected to have such disease by imaging during screening.
- 9. Has clinically significant corneal disease.
- 10. Has any evidence of severe or uncontrolled systemic diseases (including uncontrolled hypertension, and active bleeding diatheses or active infection including hepatitis B, hepatitis C and HIV infection), psychiatric illness/social situations, substance abuse, or other factors which in the Investigator's opinion makes it undesirable for the subject to participate in the study or which would jeopardize compliance with the protocol. Screening for chronic conditions is not required.
- 11. Is a lactating mother (women who are willing to temporarily interrupt breastfeeding will also be excluded), or pregnant as confirmed by pregnancy tests performed within 7 days prior to enrollment.
- 12. Has clinically active spinal cord compression or brain metastases, defined as untreated and symptomatic, or requiring therapy with steroids or anticonvulsants to control associated symptoms. Subjects with treated brain metastases that are no longer symptomatic for 4 weeks before enrollment and who require no treatment with steroids may be included in the study if they have recovered from the acute toxic effect of radiotherapy. A minimum of 2 weeks must have elapsed between the end of whole brain radiotherapy and study enrollment (1 week for stereotactic radiotherapy).

- 13. Has unresolved toxicities from previous anticancer therapy, defined as toxicities (other than alopecia) not yet resolved to NCI-CTCAE version 5.0, grade ≤1 or baseline. Subjects with chronic grade 2 toxicities may be eligible per the discretion of the Investigator.
- 14. Has a concomitant medical condition that would increase the risk of toxicity, in the opinion of the Investigator.
- 15. Has known hypersensitivity to either the drug substances or inactive ingredients in the drug product.
- 16. Has multiple primary malignancies within 3 years, except adequately resected non-melanoma skin cancer, curatively treated in-situ disease, or other solid tumors curatively treated.

## 5. STUDY TREATMENT(S)

# 5.1. Assigning Subjects to Treatment Group(s)/Sequences and Blinding

### **5.1.1.** Treatment Group(s)/Sequences

See Section 3.1.1.1 to 3.1.1.4.

[figure not shown]
### 5.1.2. Method of Treatment Group(s)/Sequences Allocation

See Section 3.1.1.1 to 3.1.1.4.

#### 5.1.2.1. Enrollment

Subject enrollment is conducted at central interactive response technology (IRT). Enrollment process is described in Figure 5.1.

**Figure 5.1:** Subject Enrollment Process

HER3 = human epidermal growth factor receptor 3; IRT = interactive response technology; RECIST = Response Evaluation Criteria in Solid Tumors

Investigators will maintain a confidential screening log of all potential study subjects that includes limited information of the subjects, date and outcome of screening process.

Investigators will be expected to maintain an Enrollment Log of all subjects enrolled and screen failed in the study indicating their assigned Subject Number. The unique Subject Number will be assigned by IRT for all subjects who provide written informed consent for tumor screening.

Each subject will be provided with information about the study, will have all questions answered to their satisfaction, and will sign and date an ICF. This must be completed before any study-specific procedures are performed. Separate Informed consent must be obtained for the examination of HER3 expression in the tumor tissue. Additional information about informed consent procedures is provided in Section 15.3.

After obtaining an informed consent for tumor screening, the Investigator or designee should perform a tumor biopsy or should request archive tumor tissue. Tumor tissue (fresh or archived) must be sent to a central laboratory selected by the Sponsor to determine HER3 expression. Results of HER3 IHC testing will be reported to the Investigator by the central laboratory. During the Dose Expansion Part, subjects with HER3 positive expression determined using an archived tumor tissue sample will require a fresh tumor biopsy prior to study treatment. Fresh tumor tissue obtained from this biopsy must be sent to the central laboratory selected by the Sponsor to determine HER3 expression; these results are not required for study eligibility. The Investigator or designee must also send all computed tomography (CT) or magnetic resonance imaging (MRI) scans performed within 28 days of enrollment to the central imaging CRO selected by the Sponsor for confirmation of measurable disease per RECIST version 1.1. The central imaging CRO review results will be reported to the Investigator to confirm eligibility.

After obtaining written informed consent (Section 15.3), the Investigator or designee must determine if all inclusion and exclusion criteria have been satisfied, including obtaining a fresh tumor biopsy, if required. A subject is considered enrolled in the study once the Investigator enters all required data of eligible subjects into the IRT (IWRS). After the confirmation of the eligibility of the subject, the Investigator or designee enters subject data in the IRT. The date of enrollment is defined as the date that the subject is confirmed eligible in the IRT.

When the subject is enrolled, administration dose and dosing schedule will be assigned by the IRT. Investigators must confirm the dosing regimen assigned by the IRT before administration of U3-1402.

For screen fail subjects, Investigators must explain the reason of screen failure to the subject and then record the date of screen failure and the reason of failure in the IRT.

Electronic case report form (eCRF) will be created for all subjects who have signed informed consent for participation in the study. An eCRF will not be created for subjects who have signed informed consent for examination of the tumor only. Data for all study visits will be recorded on the eCRF for subjects who receive study drug. Only minimal data will be recorded as screening failures on the eCRF for subjects who do not meet eligibility and/or do not receive study drug. Further data, such as AEs, will not be collected from subjects once they are considered screen failures or have decided to withdraw prior to receiving study drug.

#### 5.1.3. Blinding

This study is open-label and no blinding will be performed.

#### **5.1.4.** Emergency Unblinding Procedure

Not applicable.

## 5.2. Study Drug(s)

### 5.2.1. Description

The head of the study center in Japan or the Investigator must ensure that the investigational product will be used only in accordance with the protocol.

The U3-1402 drug product is an containing 50 mg of U3-1402 in 2.5 mL solution in a containing 50 mL solution in a containing 50 mL solution in a containing 50 mL solution in

#### 5.2.2. Labeling and Packaging

U3-1402 will be supplied by the Sponsor. Study drug supplies will be packaged in cartons containing 10 vials of U3-1402 Injection 50 mg/2.5 mL. The packaging will be clearly labeled "For Clinical Study Use Only" and will show the display name of the investigational product, the lot number, storage condition and other required information in accordance with local regulations.

#### 5.2.3. Preparation

The drug for IV infusion is prepared by dilution of the required volume of the drug product (calculated based on the subject's body weight) in a volume of 250 mL 5% dextrose in water (D5W). Prepared medicinal solutions should be used immediately. The preparation will be conducted in accordance with the Pharmacy Instruction provided by the Sponsor. Procedures for proper handling and disposal of anticancer drugs should be followed in compliance with the standard operating procedures (SOPs) of the study site.

#### 5.2.4. Administration

U3-1402 will be infused as a continuous IV infusion over approximately 90 minutes on Day 1 of Cycle 1. If there are no infusion-related reactions after the initial dose, subsequent doses of U3-1402 will be infused over approximately 30 minutes on Day 1 of each subsequent cycle. Refer to Table 5.2 for additional information on drug administration following infusion related reactions. The subject's weight at Screening (baseline) will be used to calculate the initial dose. The subject's weight will be determined at the beginning of each cycle. If the subject's weight changes more than 10% from the baseline weight, the dose will be recalculated using the new weight. This weight will become the new baseline weight for dosing.

#### **5.2.5. Storage**

Drug supplies must be stored in a secure, limited access storage area under the storage conditions listed below:

• Stored CCI

If storage conditions are not maintained per specified requirements, Sponsor or Contract research organization (CRO) should be contacted.

#### 5.2.6. Drug Accountability

When a drug shipment is received, the Investigator or designee will check the amount and condition of the drug, check for appropriate local language in the label, and check the drug expiration date. In addition, the Investigator or designee shall contact Sponsor as soon as possible if there is a problem with the shipment.

A Drug Accountability Record will be provided for the investigational product. The record must be kept current and should contain the dates and quantities of drug received, subject's information for whom the investigational product was dispensed, the date and quantity of investigational product dispensed and the remaining quantity.

At the end of the study, or as directed, all unused U3-1402 will be returned to a designee as instructed by Sponsor or will be destroyed. Investigational Product will be returned only after the study monitor has completed a final inventory to verify the quantity to be returned. The return of Investigational Product must be documented, and the documentation included in the shipment. At the end of the study, a final Investigational Product reconciliation statement must be completed by the Investigator or designee and provided to the Sponsor. Unused drug supplies may be destroyed by the supervisor of investigational products in Japan and Investigator in the US when approved in writing by Sponsor, and after the Sponsor has received copies of the site's drug handling and disposition SOPs.

All investigational product inventory forms must be made available for inspection by a Sponsor authorized representative or designee and regulatory agency inspectors. The supervisor of investigational products in Japan and Investigator in the US are responsible for the accountability of all used and unused study supplies at the site.

### **5.2.7.** Retention Samples

Not applicable.

#### **5.3.** Control Treatment

Not applicable.

## **5.4.** Dose Interruptions and Reductions

Specific criteria for dose interruption, re-initiation, reduction and/or discontinuation of U3-1402 are listed in Table 5.2. Doses may also be interrupted for other AEs per Investigator discretion, and supportive therapy may be administered in accordance with local practice guidelines. All dose interruptions or dose modifications must be recorded on the AE and drug administration eCRF pages.

Dose modifications are applicable only to TEAEs that are assessed as related to use of U3-1402 by the Investigator(s). For non-drug-related TEAEs, follow standard clinical practice. Appropriate external experts such as a cardiologist, pulmonologist, etc, should be consulted as deemed necessary.

#### **5.4.1.** Dose Interruptions

The dose can be interrupted for up to 4 weeks from the planned date of administration (ie, 49 days from the last infusion date). If a subject is assessed as requiring a dose delay longer than 4 weeks, the subject may be withdrawn from the study following discussion and agreement between the Investigator and Sponsor.

#### 5.4.2. Dose Reductions

Two dose reductions of U3-1402 may be permitted. Further dose reductions may be considered after discussion and agreement between the Investigator and Sponsor. Dose reductions below 1.6 mg/kg (or equivalent Q2W dose level; Table 5.1) will not be permitted.

### Dose Reduction(s) for Q3W Dosing Schedule

If dose reduction is required, U3-1402 dosing should be reduced by 1 dose level at a time (Table 5.1). Once the dose of U3-1402 has been reduced due to an AE, all subsequent cycles should be administered at that lower dose level unless further dose reduction is required.

### Dose Reduction(s) for Q3W Dosing Schedule with Up-Titration Cohorts

If dose reduction is required, U3-1402 dosing should be reduced by 1 dose level at a time (Table 5.1). Once the dose of U3-1402 has been reduced due to an AE, all subsequent cycles should be administered at that lower dose level unless further dose reduction is required. In addition, no further up-titration will be permitted.

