<sup>a Additional dose levels may also be considered based on review of available safety, tolerability, and pharmacokinetic data in this and other studies with the investigational agent.

subject in the new cohort will be based on an updated BLRM using DLT outcome data from all assessed doses. Subject ongoing will continue treatment at their assigned dose level.

Subjects can be backfilled (added) to lower doses previously proven to be safe at any point during dose escalation.

To better understand the safety, tolerability, PK or preliminary activity of U3-1402, additional patients may be enrolled to preceding dose levels, or to intermediate dose level before or while proceeding with further dose escalation.

The Dose Escalation Part will be stopped according to the following rules:

- i. at least 6 evaluable subjects have been enrolled at the MTD level with at least 18 evaluable subjects in total enrolled in the Dose Escalation Part
- ii. at least 9 evaluable subjects have been enrolled at a particular dose level, the model recommends continuing at the same dose level, and the posterior probability of the DLT rate falling within the target DLT interval is ≥50%. The target DLT interval is defined as 16% <DLT rate ≤33%
- iii. DLT assessment with at least 3 evaluable subjects at the maximum possible dose level with upper limit of 95% credible interval for posterior probability of DLT rate is lower than 33%
- iv. the initial dose level is too toxic.

Cohorts may be expanded at any dose level or at the MTD for further elaboration of safety, or PK parameters as required.

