### **Dose Finding Cohort 3 (Q3W Dosing with Up-titration)**

U3-1402 administered via IV infusion Q3W in 21-day cycles with an up-titration of U3-1402 dose on Day 1 of the first 3 cycles as described below.

**Table 3.2:** Dose Finding Cohort 3 Dosing Schedule

Cycle	U3-1402 Dosage
1	3.2 mg/kg IV infusion Q3W
2	4.8 mg/kg IV infusion Q3W
3	6.4 mg/kg IV infusion Q3W
Subsequent cycles	6.4 mg/kg IV infusion Q3W

IV = intravenous; Q3W = once every 3 weeks.

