### 3.1.7. Dose-limiting Toxicities

A DLT is defined as any TEAE not attributable to disease or disease-related processes that occurs during the DLT evaluation period (Day 1 to Day 21 in Cycle 1 of Dose Escalation Part) and is Grade 3 or above according to National Cancer Institute Common Terminology Criteria for Adverse Events (NCI-CTCAE) version 5.0, with the exceptions as defined below:

For hematological toxicities, a DLT is defined as follows:

- Grade 4 neutrophil count decreased lasting >7 days, neutrophil count decreased that requires standard therapies, such as colony stimulating factor (CSF)
- Grade ≥3 febrile neutropenia
- Grade 4 anemia
- Grade 4 platelet count decreased

- Grade  $\geq$ 3 platelet count decreased lasting >7 days
- Grade ≥3 platelet count decreased with clinically significant hemorrhage
- Grade 4 lymphocyte count decreased lasting ≥14 days

For hepatic organ toxicities, a DLT is defined as follows:

- Serum aspartate aminotransferase (AST) or serum alanine aminotransferase (ALT) >20  $\times$  upper limit of normal (ULN)
- AST or ALT >5 × ULN, if accompanied by blood bilirubin >1.5 × ULN
- In subjects without liver metastases, AST or ALT  $>5 \times$  ULN lasting >3 days
- In subjects with liver metastases, AST or ALT >5 × ULN lasting >3 days, if the baseline level was <3 × ULN
- In subjects with liver metastases, AST or ALT  $> 8 \times ULN$  lasting > 3 days, if the baseline level was  $> 3 \times ULN$

For non-hematological, non-hepatic major organ toxicities, a DLT is defined as follows:

- Symptomatic congestive heart failure (CHF)
- Left ventricular ejection fraction (LVEF) decline to <40% or >20% drop from baseline
- Other Grade ≥3 non-hematological, non-hepatic major organ toxicities

The following TEAEs are NOT considered DLTs:

- Grade 3 fatigue lasting <7 days
- Grade 3 nausea, vomiting, diarrhea, or anorexia that has resolved to Grade ≤2 within 3 days
- Isolated laboratory findings not associated with signs or symptoms including Grade 3/4 serum alkaline phosphatase (ALP) increased, hyperuricemia, serum amylase increased, and lipase increased, and Grade 3 hyponatremia lasting <72 hours developed from Grade 1 at baseline
- Grade 3 lymphocyte count decreased

If any of the above toxicities is observed during the DLT evaluation period, whether the toxicity is regarded as DLT will be determined based on consultation between the Investigator and Sponsor.

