	Grade 3 Prolonged (eg, not rapidly responsive to symptomatic medication and/or brief interruption of infusion); recurrence of symptoms following initial improvement; hospitalization indicated for clinical sequelae  Grade 4 Life-threatening consequences; urgent intervention indicated	Administration of U3-1402 should be discontinued immediately and permanently.  Urgent intervention indicated. Antihistamines, corticosteroids, epinephrine, bronchodilators, vasopressors, IV fluid therapy, oxygen inhalation etc, must be administered as clinically indicated.	
Fatigue/ Asthenia	Grade 3	Delay dose until resolved to ≤Grade 1 or baseline values, then:  If resolved to ≤Grade 1 or baseline values in ≤14 days, resume U3-1402.  If resolved to ≤Grade 1 or baseline values in >14 days, U3-1402 may be resumed after discussion and agreement reduce U3-1402 by 1 dose level and resume.	
Blood and lymphatic			
Neutrophil count decreased	Grade 3 (500 to <1000/mm  ; 0.5-1 × 10  /L)	Delay dose until resolved to ≤Grade 2, then resume U3-1402.	
a contract	Grade 4 (<500/mm  ; <0.5 × 10  /L)	Delay dose until resolved to ≤Grade 2, then reduce U3-1402 by 1 dose level.	

Table 5.2: Dose Delay Criteria and Dose Reduction for U3-1402 (Continued)

	Worst Toxicity NCI- CTCAE Version 5.0 Grade (unless otherwise specified)	Schedule Modification for U3-1402
Febrile neutropenia (ANC <1000/mm³;	Grade 3	Delay dose until resolved; then resume U3-1402. Consider reducing U3-1402 by 1 dose level.
<1 × 10  /L, fever >38.3°C or a sustained		Consider administration of granulocyte colony-stimulating factor as prophylaxis for all subsequent cycles and according to local guidelines.
temperature of ≥38°C for more	Grade 4	Delay dose until resolved, then reduce U3-1402 by 1 dose level and resume.
than 1 hour)		Administer granulocyte colony-stimulating factor as prophylaxis for all subsequent cycles and according to local guidelines.
Anemia	Grade 3 (Hemoglobin <8.0 g/dL)	Delay dose until resolved to ≤Grade 2 or baseline; then resume U3-1402.
		For recurrent anemia, delay dose until resolved ≤Grade 2 or baseline, then reduce U3-1402 by 1 dose level and resume.
		Consider packed red blood cell transfusion according to institutional guidelines.

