	Grade 4 (Life-threatening consequences; urgent intervention indicated)	Delay dose until resolved to ≤Grade 2 or baseline, then reduce U3-1402 by 1 dose level and resume.  Consider transfusion according to institutional guidelines.
Platelet count decreased	Grade 3 (Platelet <50 - 25 × 10  /L)	Delay dose until resolved to ≤Grade 1, then:  If resolved in ≤14 days, resume U3-1402.  If resolved in >14 days, U3-1402 may be resumed.  Consider reducing U3-1402 by 1 dose level.  Consider platelet transfusion according to institutional guidelines.
	Grade 4 (Platelet <25 × 10  /L)	Delay dose until resolved to ≤Grade 1, then reduce U3-1402 by 1 dose level and resume.  Consider transfusion according to institutional guidelines.
Lymphocyte Count Decreased	Grade 4 (<0.2 × 10  /L)	Delay dose until resolved to ≤Grade 2, then: If resolved in ≤14 days, resume U3-1402. If resolved in >14 days, reduce U3-1402 by 1 dose level and resume.
Cardiac disorders		
Heart failure	Grade ≥2 (Symptoms with moderate activity or exertion)	Cardiologist consult as necessary.  Delay dose until resolved to ≤Grade 1, then reduce U3-1402 by 1 dose level.
Ejection fraction decreased	Decrease in LVEF 10% to 20% (absolute value), but LVEF >45%	Continue treatment with U3-1402.
	LVEF 40% to ≤45% and decrease is <10% (absolute value) from baseline	Continue treatment with U3-1402. Repeat LVEF assessment within 3 weeks.

Table 5.2: Dose Delay Criteria and Dose Reduction for U3-1402 (Continued)

	Worst Toxicity NCI- CTCAE Version 5.0 Grade (unless otherwise specified)	Schedule Modification for U3-1402
	LVEF 40% to ≤45% and decrease is ≥10% to 20% (absolute value) from baseline	Delay U3-1402 dosing. Repeat LVEF assessment within 3 weeks. If LVEF has not recovered to within 10% (absolute value) from baseline, discontinue subject from study treatment.
	LVEF <40% or >20% drop from baseline	Delay U3-1402 dosing.  Repeat LVEF assessment within 3 weeks; if LVEF <40% or >20% (absolute value) drop from baseline is confirmed, discontinue U3-1402.  Cardiologist consult as necessary.

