	Worst Toxicity NCI- CTCAE Version 5.0 Grade (unless otherwise specified)	Schedule Modification for U3-1402		
Pulmonary toxicity	Grade 3 or 4	Permanently discontinue subject from study treatment.		
1 dimonary toxicity	Grade 5 of 1	Toxicity Management:		
		Hospitalization is required.		
		Promptly initiate empiric high-dose methylprednisolone IV treatment (eg, 500-1000 mg/day for 3 days), followed by at least 1.0 mg/kg/day of prednisone (or equivalent) for a minimum of 14 days or until complete resolution of clinical symptoms and chest CT findings, followed by gradual taper over at least 4 weeks.		
		Reimage as clinically indicated.		
		If still no improvement within 3 to 5 days,		
		
 
Reconsider additional work-up for alternative etiologies as described above.
 
		
		
 
Consider other immuno-suppressants and/or treat per local practice.
 
		
Endocrine disorders				
Endocrine	Grade 3	Delay dose until resolved to ≤Grade 2, then:		
disorders		If resolved in ≤14 days, resume U3-1402.		
		If resolved in >14 days, U3-1402 may be resumed after discussion and agreement between the Investigator and Sponsor.		
	Grade 4	Discontinue subject from U3-1402.		
Eye disorders				
Ocular	Grade 3	Delay dose until resolved to ≤Grade 2, then: If resolved in ≤7 days, resume U3-1402.		
		If resolved in >7 days, then reduce U3-1402 by 1 dose level.		
		Ophthalmologist consultation as clinically indicated.		
	Grade 4	Discontinue subject from U3-1402. Ophthalmologist consult as necessary.		
Renal and urinary d	isorders			
Creatinine increased	Grade 3 (>3.0 × baseline; >3.0 - 6.0 × ULN)	Delay dose until resolved to ≤Grade 1 or baseline, then reduce U3-1402 by 1 dose level.		
	Grade 4 (>6.0 × ULN)	Discontinue subject from U3-1402.		

Table 5.2: Dose Delay Criteria and Dose Reduction for U3-1402 (Continued)

	Worst Toxicity NCI- CTCAE Version 5.0 Grade (unless otherwise specified)  Schedule Modification for U3-1402		
Hepatobiliary disord	lers		
AST or ALT increased without TBL increased	Grade 2 (>3.0 - 5.0 × ULN if baseline was normal; >3.0 - 5.0 × baseline if baseline was abnormal)	Continue U3-1402. In subjects without liver metastasis, monitor AST/ALT 24 to 72 hours later, and continue regular monitoring until resolution.	
	if baseline was normal; >5.0 - 20.0 × baseline if	Delay U3-1402 dose until resolved to ≤Grade 1, then: If resolved in ≤7 days, resume U3-1402. If resolved in >7 days, then reduce U3-1402 by 1 dose level.	

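### In up-titration Cohort 3, no rule holds the next dose step after an event of DLT grade and duration that ends in resumption without a dose reduction

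*Combined protocol and SAP*

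**What the plan says.** **Schedule.** Section 3.1.4 describes Cohort 3 as Q3W dosing "with an up-titration of U3-1402 dose on Day 1 of the first 3 cycles". Table 3.2 gives 3.2 mg/kg in Cycle 1, 4.8 in Cycle 2 and 6.4 from Cycle 3. No toxicity condition is attached to either step.

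**Stop rule.** Under the heading for up-titration cohorts, Section 5.4.2 says that a dose reduced for an AE stays at the lower level, and then: "In addition, no further up-titration will be permitted". The stop therefore depends on a reduction having been made.

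**What Table 5.2 requires** (related events only, per Section 5.4):
- Grade 3 platelets: wait for Grade 1 or better, then "If resolved in ≤14 days, resume U3-1402". If recovery takes longer than 14 days, resumption is allowed and a reduction is only to be considered.
- Grade 3 AST or ALT without raised bilirubin: wait for Grade 1 or better, then "If resolved in ≤7 days, resume U3-1402. If resolved in >7 days, then reduce U3-1402 by 1 dose level".
- Grade 3 febrile neutropenia: "Delay dose until resolved; then resume U3-1402. Consider reducing U3-1402 by 1 dose level".

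**DLT criteria.** Section 3.1.7 lists Grade 3 or higher "platelet count decreased lasting >7 days", "Grade ≥3 febrile neutropenia", and, in subjects without liver metastases, AST or ALT above 5 × ULN for more than 3 days. The section applies to Days 1 to 21 of Cycle 1 in the Dose Escalation Part.

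**The concern.** The stop rule shows that the authors meant to prevent titrating upward after toxicity. It covers only the subjects whose dose is reduced. A subject whose event is just as serious by the protocol's own criteria, but whose row in Table 5.2 ends in resumption, falls outside it. Read with Table 3.2, that subject is next due the higher dose.

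In a flat Q3W cohort the missing restart dose does no harm, because resuming can only mean the same dose. In Cohort 3 it decides between 3.2 and 4.8 mg/kg, or between 4.8 and 6.4 mg/kg. At stake is the safety of the individual subject, and also uniform conduct: if sites read the silence differently, the safety assessment of the titration schedule mixes two regimens. Thrombocytopenia, the clearest example, is common with this drug: Section 1.2.3 reports decreased platelet count in 36 of 56 treated subjects (64.3%). That figure covers all grades, doses and parts, so it shows relevance and is not a rate for Cohort 3.

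**Working it through.** The plan gives no figure of its own to reproduce. The check compares the rules and computes the size of the steps.

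**1. Dose steps (Table 3.2).** Relative step = next dose / current dose − 1.
- Cycle 1 to 2: 4.8/3.2 − 1 = +50%
- Cycle 2 to 3: 6.4/4.8 − 1 = +33%
- Flat Q3W cohorts: 0%

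**2. Can one event meet a 3.1.7 criterion and still need no reduction under Table 5.2?**

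| Event | Section 3.1.7 | Table 5.2, no reduction required | Both can hold? |
|---|---|---|---|
| Grade 3 platelets | more than 7 days at Grade ≥3 | Grade ≤1 reached within 14 days (later: reduction optional) | yes |
| AST/ALT >5 × ULN, no liver metastases | more than 3 days | Grade ≤1 reached within 7 days | yes |
| Grade 3 febrile neutropenia | any duration | always; reduction optional | yes |

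For the first two rows the clocks differ. Section 3.1.7 counts days at the severe level, while Table 5.2 counts time to recovery. Table 5.2 does not state when its clock starts in these rows; I assume onset. On that basis the overlap for platelets is Grade 3 for at least 8 days with recovery by day 14, and for AST/ALT it is at least 4 days with recovery by day 7. Grade 4 events are not part of the gap: Table 5.2 requires a reduction for Grade 4 platelets and Grade 4 febrile neutropenia, and discontinuation for Grade 4 AST/ALT.

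**3. Example without any delay.** Grade 3 platelets on Days 8 to 17 of Cycle 1 last 10 days, which is more than 7. Grade 1 or better by Day 21 is 13 days after Day 8, which is within 14. No reduction is required, so the stop rule is not triggered. Table 3.2 then gives 4.8 mg/kg on Day 22, where the event occurred at 3.2 mg/kg.

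**4. Does another rule hold the step?**
- Section 5.1.2.1 has the IRT assign dose and schedule, which the investigator confirms before dosing.
- Section 5.4 lets the investigator interrupt treatment for other AEs, and Section 5.8 allows discontinuation. Neither provides for repeating a dose level.
- Section 15.5 allows deviations only to remove an immediate hazard.
- Elsewhere the restart dose is named: Table 5.2 keeps the dose unchanged after Grade 1 pulmonary toxicity that resolves within 28 days, and Table 17.11 uses the same dose after Grade 1 COVID-19. The three rows above do not name it.

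**5. Next dose if the step is held.** 3.2 mg/kg instead of 4.8 after Cycle 1, and 4.8 instead of 6.4 after Cycle 2: 0% in both cases. A one-level reduction from the dose received gives 1.6/3.2 − 1 = −50% or 3.2/4.8 − 1 = −33%.

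**The case against.** **DLT criteria are not rules for individual dosing.** They feed the escalation model, and Table 5.2 governs individual subjects. In flat Cohort 2 the same events also end in resumption, at 6.4 mg/kg, which Cohort 3 never exceeds. This stands as a limit on the point. A reader might infer that the protocol escalates subjects after a formal DLT. It does not say so: Section 3.1.7 does not apply to Dose Finding, and a Cycle 2 event lies outside its window in any part. The criteria serve only as a measure of severity. What differs in Cohort 3 is the direction of change: the dose can go above the one at which the event occurred.

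**The increase is inferred from silence.** A reader might conclude that the protocol requires it. The rows name no dose, and for febrile neutropenia, and for platelets beyond 14 days, a reduction is open to the investigator and would stop titration. What the text supports is that nothing prevents the step, and that IRT assignment and the deviation rule favour following the schedule.

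**Other cohorts also step up.** In mg/kg per infusion, Cohort 4 goes from 4.2 to 6.4 (+52%) and Cohort 5 from 3.2 to 4.8 (+50%) at Cycle 4. The interval lengthens at the same time: 4.2/2 = 2.10 against 6.4/3 = 2.13 mg/kg per week, and 3.2/2 = 1.6 against 4.8/3 = 1.6. Table 5.1 treats these as the same dose level, so they are not comparable increases.

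**A reduction might give back the same dose.** This could be inferred if the reduction were counted from the scheduled dose. Section 5.4.2 speaks of a lower dose level, so the dose received is the natural base. One clarifying sentence is enough.

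**Few subjects are affected.** The cohort is provisional, has about 12 subjects, and every listed expansion cohort is flat Q3W. By the August 2018 cut-off, 14 subjects had already been treated in Dose Expansion (Section 1.2.3), so few or none may still be titrating. This stands, and it is why the point is rated as a cheap improvement.

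**Conclusion.** The gap is real and narrow. In Cohort 3 the stop rule covers the reduction branch only. At least three kinds of related event that reach the severity criteria of Section 3.1.7 can end in resumption with no required reduction, and no passage then holds the scheduled increase of 50% or 33%.

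This rests on using Section 3.1.7 as a yardstick and, for the time windows, on counting recovery from onset. It is bounded by the recovery required before restart, by the 6.4 mg/kg ceiling, and by the size and provisional status of the cohort. It would also apply to any further up-titration regimen added under Section 3.1.4. A reader might want an expected number of affected subjects, but the documents do not support one: the prior in Section 11.7.2 is deliberately weak and concerns any DLT, not the events described here. No Dose Expansion hypothesis is touched.

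**What to change.** Add to Section 5.4.2 for up-titration cohorts:

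> If a U3-1402-related event meets the grade and duration criteria in Section 3.1.7 and the dose is not reduced, treatment resumes at the last dose received and the scheduled step is not taken at that cycle. The step may be taken at a later cycle if no such event recurs. Any dose reduction is counted from the last dose received.

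Set the IRT to match. The text deliberately says nothing about other events, so the investigator keeps the present latitude there.

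The cost is three sentences and one IRT rule. Affected subjects reach 6.4 mg/kg at least one cycle later; all other Cohort 3 subjects keep the planned regimen. If the sponsor does intend the step to be taken after such events, Section 5.4.2 should say so.
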